6.8 Unscheduled Visits

Subjects may require an evaluation at times other than the scheduled visits. An unscheduled visit should only be conducted when the subject reports problems that are related to safety, the IUS or study participation, or if repeat laboratory testing is required. In such circumstances, the unscheduled visit should be performed by a study clinician to review any change in medical history and perform any examination and testing as clinically indicated.

6.9 Diagnostic Ultrasound Examinations

Diagnostic ultrasound examinations may be required during the study to evaluate pregnancy (see Appendix B), missing IUS strings (see Appendix C), confirmation of IUS location or possible IUS related adverse events. Any time an ultrasound examination is performed for diagnostic purposes, the image must be documented in a photo or digital image to be included in the source documentation. A copy of the image documentation should be forwarded within 5 business days for a verifying review by the Sponsor as described in the Study Reference Manual. All ultrasound findings should be documented as follows:

- Printed image(s) with the subject's study number on the image
- Indication, impression and plan related to the images written in the source documentation

All ultrasound examination documentation should be maintained with the subject's study source documentation.

For details regarding the sponsor review of study-related ultrasound exams see the Study Reference Manual.

6.10 Substudy Procedures

6.10.1 Treatment PK Substudy

Subjects in this substudy will consist of two cohorts based on BMI. Forty non-obese (BMI <30 kg/m²) women will be randomized by the IVRS separately from the main study subjects in a 1:1 ratio to LNG20 or Mirena. In addition, twenty obese (BMI ≥ 30 kg/m²) women will receive the LNG20. Blood samples will be collected for plasma levonorgestrel levels at the Enrollment Visit before insertion of the IUS, and then at Days 7 and 14, and Months 1, 3, 6, 9, 12 18, 24, 30 and at

Early Discontinuation. A window of plus or minus 1 day is allowed for the Week 1 and 2 visits, and a window of plus or minus 3 days is allowed for the subsequent month visits to allow for scheduling. The PK sampling will require three extra study visits for blood draws only on Days 7 and 14 (no other study procedures are required at those visits), and for blood draw and Month 9 Contact procedures. All other PK sampling visits should be performed in conjunction with the corresponding primary study visits. For details regarding PK blood sample collecting, processing and shipping, see the PK Lab Manual.

6.10.2 Endometrial Thickness Substudy

Subjects in this substudy will be assigned the LNG20. Endometrial thickness assessments will be made at Enrollment (pre-IUS insertion), Month 12, Month 60 and Month 120 study visits. The assessment at Enrollment should occur after IVRS assignment to LNG20 and before IUS insertion. If IUS removal is planned at the same study visit, the endometrial thickness assessment should occur before IUS removal. Endometrial thickness should not be assessed at any other visits, including an early Discontinuation Visit (unless that visit is occurring at Month 12, Month 60 or Month 120). Endometrial thickness is defined as the maximal dimension of the endometrial cavity in the anterior-posterior plane of the uterus, including all contents of the endometrial cavity, and will be measured in a longitudinal view of the uterine cavity using transvaginal sonography.

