1.2 Medicines360 Levonorgestrel-Releasing Intrauterine System

The levonorgestrel IUS (LNG20) that Medicines360 has developed consists of a T-shaped polyethylene frame (T-body) with a steroid reservoir around the vertical stem. The steroid reservoir is covered with a polydimethylsiloxane membrane which controls the release rate of

levonorgestrel from the reservoir. The LNG20 reservoir contains 52 mg levonorgestrel; providing an initial release rate of approximately 20 mcg/day. A polypropylene monofilament blue thread is attached to the end of the vertical stem. Please refer to the Investigator's Brochure for full details on the components of LNG20.

LNG20 has been investigated in a multi-center, single-blind randomized trial in Europe to assess the therapeutic equivalence in terms of efficacy and safety compared to Mirena in patients with menorrhagia. Enrollment of 280 subjects was completed in January, 2009 and 50% were randomized to LNG20. A review of all safety data supports that LNG20 was generally well tolerated in female subjects with menorrhagia. Serious adverse events (SAEs) collected during the reporting period did not reveal any new safety concerns and did not change the overall risk-benefit evaluation for LNG20. Adverse event-related removals of the IUS occurred in five women (three LNG20, two Mirena). The three LNG20 removals were related to ovarian cysts (one of these three subjects required hospitalization). The two Mirena removals followed development of abdominal and peripheral edema in one subject, and reported nervousness, chest tension, abdominal pain, and hypertension in a second subject. There were 5 SAEs reported in the LNG20 arm. One SAE was assessed as possibly related (Ovarian Cyst) and 3 were assessed as unrelated (Headache, Lumbar Disc Herniation, and Abdominal Colic). An additional unrelated event (Pregnancy) was reported as a SAE because it was an important event. Expulsion rates reported for the first year of use were 4.3% for LNG20 and 3.6% for Mirena.

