Subjects will receive detailed instructions on how to record vaginal bleeding, dysmenorrhea, and other contraceptive use in a daily diary during the first 24 months of study participation. Thereafter, only other contraceptive use will continue to be recorded daily on a diary for the remainder of study treatment in addition to the information collected at each study visit. After 24 months, bleeding and dysmenorrhea information only will be obtained for the remainder of study treatment via interviews by study staff during each study follow-up visit and contact (every 3 months) during treatment.

In addition, Levonorgestrel plasma levels will be obtained for all subjects at six month intervals and at IUS discontinuation visit beginning with Month 36 until Protocol Version 9 when thereafter, levonorgestrel plasma levels will be obtained in all subjects at IUS discontinuation and also annually in all women enrolled prior to 31May2011.

The Sponsor intends to retain all IUSs that are removed or expelled (when possible) and analyze an appropriate sample of these systems.

The following substudies will be performed at selected sites:

- Levonorgestrel PK data will be obtained in a subset of approximately 60 subjects (20 non-obese LNG20 subjects, 20 non-obese Mirena subjects and 20 obese LNG20 subjects). In

addition to all procedures outlined in Section 6 for the concomitant primary study visits, LNG plasma samples will be obtained at Enrollment (pre-IUS insertion), Weeks 1 and 2, and Months 1, 3, 6, 9, 12, 18, 24 and 30 after IUS insertion (includes three extra visits at Weeks 1 and 2, and Month 9, not included in the main study). These subjects will be required to give informed consent for participation in the levonorgestrel PK subset (See Section 4.4).

- A subset of 60 subjects assigned to LNG20 and completing 121 months of study treatment will have levonorgestrel samples obtained at various timepoints after IUS removal to characterize the LNG elimination profile. Each subject in this subset will be randomized to one timepoint (one extra visit) post-IUS removal (24 hours, 48 hours, 7 days or 14 days) such that fifteen subjects are randomized to each timepoint.
- A subset of 60 women assigned to LNG20 at selected sites will have transvaginal ultrasound evaluations at enrollment (pre-IUS insertion), 1 year, 5 years and 10 years (pre-IUS removal) to assess changes in endometrial thickness.

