6.3 Screening/Enrollment Visit

Screening is considered to start with the signing of the Informed Consent Form by the subject. Although the Screening and Enrollment Visits may occur during one visit, the Screening procedures may be performed over multiple days. The Enrollment Visit is considered to be on the date the subject is assigned through the IVRS. Screening test results are not required to be available prior to the Enrollment Visit.

Scheduling of the Enrollment Visit must take the following schemes into account:

- When switching from an oral, transdermal or vaginal hormonal contraceptive, the subject should continue that method after the study IUS insertion until the end of the current cycle. If using the contraceptive continuously (without a hormone free interval), then discontinue 7 days after IUS insertion. When possible, the Enrollment Visit should be scheduled during the hormone-free time of the cycle (i.e., “placebo week,” “patch-free week,” or “ring-free week”)
- When switching from an injectable monthly combined hormonal injection, the study IUS insertion may occur anytime within 28 days of the last injection
- When switching from non-hormonal contraception (except copper IUD), the study IUS insertion **must** be performed within the first 7 days of the menstrual cycle

- When switching from a contraceptive implant, another hormonal IUS, or a copper IUD, the study IUS insertion may occur anytime in the menstrual cycle but should occur on the same day as removal of the implant, non-study IUS, or IUD
- Women who need a screening Pap test (see section 6.11) should be scheduled for screening on a day they are expected to have minimal or no bleeding
- All enrollment procedures must be completed within 30 days of screening. If greater than thirty days, Medical Monitor approval must be obtained before rescreening or enrollment

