11.14 Endometrial Thickness

Endometrial thickness at baseline and after 1, 5 and 10 years of LNG20 use will be summarized using the ET population. Changes from baseline will also be summarized. Baseline is defined as the last non-missing value prior IUS insertion.

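### Endometrial thickness is measured with the cavity's contents included, so the planned change from baseline generally contains the IUS and understates thinning

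*Protocol*

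**What the plan says.** Protocol section 6.10.2 defines the measurement as the "maximal dimension of the endometrial cavity in the anterior-posterior plane of the uterus, including all contents of the endometrial cavity", taken in a longitudinal view by transvaginal ultrasound.

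The same section sets the timing: "Endometrial thickness assessments will be made at Enrollment (pre-IUS insertion), Month 12, Month 60 and Month 120 study visits". On the first scan it adds: "The assessment at Enrollment should occur after IVRS assignment to LNG20 and before IUS insertion". If removal is planned at a scan visit, "the endometrial thickness assessment should occur before IUS removal". Protocol section 3.1 gives the same order: "transvaginal ultrasound evaluations at enrollment (pre-IUS insertion), 1 year, 5 years and 10 years (pre-IUS removal) to assess changes in endometrial thickness". Protocol section 6.6 places planned removal in the 16-35 year group at Month 121, so a woman still using LNG20 at Month 120 has it in place when scanned.

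The object in the cavity is described in Protocol section 1.2 as a "T-shaped polyethylene frame (T-body) with a steroid reservoir around the vertical stem". No stem or reservoir diameter is given for it.

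SAP section 11.14 summarises thickness at baseline and at 1, 5 and 10 years, takes the latest pre-insertion value as baseline, and adds: "Changes from baseline will also be summarized". Protocol section 9.8 likewise compares each later year with baseline. SAP section 10.3.2 carries endometrial thickness into an exposure-response analysis. Neither document subtracts the device, measures the layers apart from it, or comments on how its presence affects interpretation.

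**The concern.** A change score is interpretable only if the same quantity is measured at both ends. Here the earlier value is generally the cavity without a device, and the later values are generally the cavity with one. The difference is then reported as a change in endometrial thickness.

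The change at 1, 5 and 10 years is a named secondary objective. As planned, a real thinning under levonorgestrel would be reported as smaller than it is, and could be reported as absent or as thickening. This is an offset rather than noise, so adding women would not remove it. The comparison that largely avoids it, between on-treatment visits within a woman, has no planned summary.

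**Working it through.** The plan states no power, precision target, standard deviation or expected thickness for this substudy, so there is no figure of its own to reproduce. The check is a measurement identity followed by illustrations.

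**Inputs from the documents.** The definition, scan times and change from baseline are as set out above. The substudy has 60 women (Protocol section 3.1). Assumed discontinuation is 20% in year 1, 19% in year 2, 17% in year 3 and 16% in each of years 4 to 10, with a stated cumulative figure of 76% (Protocol section 9.1).

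**Assumed inputs.** The documents give none of these:
- d, the anterior-posterior thickness the IUS adds where measured: 1 to 4 mm.
- Standard deviation of change: 2 to 4 mm.
- f, the share of women with an earlier device of similar thickness still in place at the baseline scan: 5% to 20%.

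**Identity.** Recorded change = (tissue on treatment + d) - tissue at baseline = true change + d.

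| True change (mm) | d = 1 | d = 2 | d = 3 | d = 4 |
|---|---|---|---|---|
| -1 | 0 | +1 | +2 | +3 |
| -2 | -1 | 0 | +1 | +2 |
| -3 | -2 | -1 | 0 | +1 |
| -4 | -3 | -2 | -1 | 0 |

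Thinning larger than d is understated by d. Thinning equal to d reads as no change, and thinning smaller than d reads as thickening.

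**Earlier device at baseline.** Mean bias = d x (1 - f). For f from 5% to 20% this is 0.95d to 0.80d.

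**Size against sampling error.** Year-1 retention gives 60 x 0.80 = 48 women. With a standard deviation of 3 mm, SE = 3/sqrt(48) = 0.43 mm, so d of 1 to 4 mm is 2.3 to 9.2 standard errors. A nominal 95% interval would cover the true change about 36% of the time at d = 1 mm and less than 1% at d = 2 mm or more. For standard deviations of 2 to 4 mm, coverage at d = 2 mm is 0% to 7%. The SAP plans no such interval; this only shows that the offset would not be lost in sampling error.

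**On-treatment contrast.** (tissue at Month 60 + d) - (tissue at Month 12 + d) = true change between those visits, provided d is similar at both scans. The same holds for Month 120.

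**Women available.**
- Month 60, annual rates compounded: 60 x 0.80 x 0.81 x 0.83 x 0.84^2 = 60 x 0.379 = 22.8.
- Month 120, stated cumulative figure: 60 x (1 - 0.76) = 14.4.
- Month 120, annual rates compounded: 60 x 0.80 x 0.81 x 0.83 x 0.84^7 = 60 x 0.159 = 9.5.

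So about 10 to 14 women would reach Month 120; the two figures differ because the annual rates do not compound to the stated total.

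**Timing.** The protocol gives November 2009 as the start of recruitment. Adding 120 months gives November 2019, after this October 2017 version, so on the planned dates all Month 120 scans lay ahead of it.

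**The case against.** The strongest reply is that the definition is explicit, the substudy is small and descriptive, no decision depends on it, and the on-treatment means will appear side by side in the planned table anyway. All of that is true and limits the consequence. It does not make the change from baseline a change in tissue, and side-by-side means over a shrinking group are not within-woman changes.

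A reader might infer more than the documents support:

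- **That every follow-up scan contains a device and no baseline scan does.** There are exceptions. For some switchers, "the study IUS insertion may occur anytime in the menstrual cycle but should occur on the same day as removal of the implant", and the same sentence extends this to a hormonal IUS or copper IUD. Protocol section 5.6 lets an earlier device come out just before insertion, so one may be present at the baseline scan. At the other end, section 6.10.2 permits a scan at an early discontinuation visit that falls at Month 12, 60 or 120; after complete expulsion it would show no IUS.
- **That the bias is constant and equals the stem diameter.** The definition takes the maximal dimension and does not require that it cross the stem. The direction follows from the text; a fixed size does not.
- **That the sign will reverse.** This happens only if thinning is smaller than the added thickness. Both quantities are unknown here, and the table shows many combinations with no reversal.
- **That splitting the results by contraceptive method at baseline would help.** Baseline states do differ, and fluid or menstrual contents may count at any scan. But with about 10 to 14 women at Month 120 the cells would be too small to use.

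**Conclusion.** The point stands in a limited form. Read as written, the plan yields a change from baseline that is biased upward by the thickness the IUS adds where measured, in most women and at all three on-treatment visits. The direction rests on the documents alone. The size rests on an unstated device contribution: over an assumed 1 to 4 mm, a 2 mm thinning would be recorded as anything from -1 to +2 mm. Earlier devices at baseline, at an assumed 5% to 20%, reduce the mean bias only to 0.95 to 0.80 of d.

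The effect is limited to a descriptive secondary outcome and the exposure-response analysis that uses it. The Pearl Index and primary efficacy are untouched.

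**What to change.** 1. In SAP section 11.14, keep change from baseline, since it is the stated outcome, but label it as including the IUS and say that it is not to be read as tissue change alone. Carry the same note to the exposure-response analysis in SAP section 10.3.2.
2. Add within-woman changes from Month 12 to Month 60 and from Month 12 to Month 120 as the on-treatment contrasts largely free of the device offset. State that they supplement the baseline contrast and do not replace it, because they miss any effect in the first year, and that the Month 120 contrast will rest on about 10 to 14 women.
3. At the remaining scheduled scans, record the anterior and posterior endometrial layers without the IUS, alongside the existing measurement. Baseline was taken with all contents included, so fluid at baseline remains a possible mismatch and should be noted.
4. For scans already taken, use subtraction of a fixed stem diameter only as a labelled sensitivity analysis, because it may over-correct where the measurement did not cross the stem.

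Items 1, 2 and 4 cost SAP wording and a few table rows. Item 3 changes a procedure defined in the protocol, so it needs a minor amendment, IRB approval where required, one data field and one extra caliper reading at visits already scheduled.

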6.10.3 Elimination PK Substudy

Subjects in this substudy will consist of those who are assigned the LNG20, have completed 121 months of IUS use, signed appropriate consent to participate in the substudy and meet the contraceptive requirements (see Section 4.4.3). Each subject will be randomized to one time point post-IUS removal at either 24 hours, 48 hours, 7 days or 14 days. There is a window of plus or minus 2 hours for the PK sampling of 24 hours and 48 hours, and a window of plus or minus 1 day for the 7 day and 14 day blood sample collection. The PK sampling day will be one extra study visit for the blood draw only and no other study procedures are required at that visit. The subject's participation in the substudy is considered complete once the PK sample is collected.

6.11 Pap Testing

Pap test criteria for study entry are outlined in Section 4.3.

General concepts:

- Eligibility Pap testing at screening must be performed in all women 20 years 6 months of age or older if no documented Pap test has been performed in the last 18 months. The enrollment visit cannot be performed until this Pap test result is available and the subject meets entry criteria
- Based on her age, if a subject will be due for a Pap test within 6 months on either side of the screening or annual study visit, a Pap test should be performed at that visit
- A copy of any Pap test or follow-up testing used for determination of study eligibility or during study follow-up must be obtained and included in the study record. If not available at the time of the visit for which the documentation is required then the Pap test should be performed per protocol
- For routine follow-up Pap testing, a Pap test obtained at an outside location within 6 months prior to the scheduled study visit can be used in place of the study Pap test as long as a written copy of results is obtained
- Pap testing is not required for Early Discontinuation if a Pap test has been done within the last 18 months and is otherwise not clinically indicated
- An abnormal Pap test that was treated before the study should still have follow-up as per the ASCCP guidelines (it is a pre-existing condition that still needs appropriate follow-up)

Pap testing at screening and study follow-up is indicated as follows:

- Women <20 years and 6 months of age: no Pap test is required at screening or any follow-up examination. Once the subject is 20 years 6 months of age, Pap testing should be performed at screening and/or “annual” visits (Months 12, 24, 36, 48, 60, 72, 84, 96, 102, 108, 114 and 120, as applicable)
- Women \geq 20 years and 6 months:
 - Screening
 - If the subject has a normal Pap test within the last 18 months then Pap testing does not need to be performed at the screening visit
 - If the subject has not had a Pap test in the past 18 months or does not have a written copy of a normal Pap test, then a Pap test should be performed at the screening visit

- If the subject has had an abnormal Pap test within the last 18 months but meets study entry criteria regarding abnormal Pap tests then one should be performed at the screening visit only if indicated as part of the routine follow-up of the abnormal Pap test (see Section 6.12)
- Follow-up Pap tests
 - For women who are currently immunosuppressed or HIV positive, Pap testing should be performed annually as long as the Pap tests remain normal (for abnormal Pap test follow-up, see section 6.12)
 - For women who have a history of treated CIN II or CIN III, Pap and HPV testing should be performed (or have been performed) at 12, 24 and 60 months after treatment as long as the Pap and HPV tests remain normal (for abnormal Pap test follow-up, see section 6.12); those women who had normal testing and are more than 60 months from treatment can undergo routine screening
 - All other women should have follow-up Pap testing every 3 years at the “annual” visit (Months 12, 24, 36, 48, 60, 72, 84, 96, 108 and 120, as applicable) as long as the Pap tests remain normal (for abnormal Pap test follow-up, see section 6.12)

High-risk (HR) HPV testing: HR HPV testing is not required but if performed as part of routine off-protocol testing then:

- Prior HR HPV tests or tests obtained during the study as part of routine screening for women ≥ 30 years will not be used to alter the timing of Pap testing.
- Reflex HR HPV testing for triage of ASCUS Pap tests in women more than 24 years of age can be used to discern if a Pap is considered normal (ASCUS/HR HPV negative) or abnormal (ASCUS/HR HPV positive)

6.12 Management of Abnormal Testing During the Study

- Any clinically significant abnormalities of the screening procedures that are exclusionary but reported after successful IUS insertion will be recorded as pre-treatment medical history and not as a protocol violation
- Clinically significant study-related results should be managed as follows:
 - Vaginal wet prep/KOH prep: treatment in accordance with current CDC guidelines for trichomoniasis, symptomatic BV, and symptomatic yeast infection

- Pap test: refer for colposcopy and treatment (if indicated) as per local or ASCCP guidelines (www.asccp.org). The study IUS should not be removed because of an abnormal Pap test or need for colposcopy or treatment
- Gonorrhea or Chlamydia: treatment in accordance with current CDC guidelines. The IUS should not be removed because of a positive test or a diagnosis of cervicitis
- Hemoglobin: a value consistent with anemia should be evaluated and treated within the local standard of care

Serum creatinine, AST, ALT, and bilirubin: any clinically significant abnormalities of the screening labs should result in appropriate evaluation/referral and be recorded as past medical history

